4.2 Pre-Treatment Procedures

Patients potentially qualifying for the study will be offered an Informed Consent to sign prior to further evaluation. Those who accept will complete study forms. Any patients not qualifying will be exited from the study as screening failures and will not be included in the efficacy and safety analyses.

A complete medical history will be obtained to determine the patient's general health status, current symptoms, frequency and dosage of their current analgesic intake etc. Kidney and Liver function tests and coagulation profile will be performed. Baseline pain scores will be established. CT examination (with and without contrast) will also be performed.

All patients will complete a run-in period to optimize patient pain meds at baseline in relation to patient pain, functionality and pain meds side effects, during which time study questionnaires (NRS, BPI-QoL, KPS, medications) will be completed.

Pre-Treatment Procedure

1. At the end of the run-in period and in the event the CT imaging is not already available, then baseline CT examination will be performed to identify the tumor size, location and extent and device accessibility as well as to evaluate the patient's ability to cooperate during the ExAblate procedure.
2. If at this point it is determined that the patient **does not** meet all Inclusion and Exclusion criteria and cannot be treated, the patient will be exited from the study. These patients will be considered screening failures, and will not be included in any of the safety or efficacy endpoint analyses.
3. If the patient meets all study criteria, the patient may have the ExAblate treatment.
4. ExAblate-treated patients will complete follow-up visits at, 1 week, and 1, 2 and 3 months.

4.3 Treatment Procedures

1. At the ExAblate treatment visit the patient will complete NRS, BPI-QoL, and KPS questionnaires and mark the primary and other sites where the most pain is felt prior to receiving any pre-treatment medications or seeing the clinician. A quiet, private location may be provided for the patient to complete the questionnaires.

2. An IV line will be positioned for the delivery of medications and will be maintained throughout the procedure. The patient may require a urinary catheter to keep the bladder empty during treatment. Monitoring of heart rate and pO2 will be maintained throughout the procedure using standard MR-compatible monitoring devices.
3. The patients' skin will be closely examined for hair in the treatment path. If necessary, the hair will be shaved around the treatment area and the skin will be cleaned, for example with alcohol, from any oil based skin product.
4. Degassed water and possibly an acoustic gel will be placed atop of the transducers' window to generate acoustic coupling.
5. Patients will be positioned on the ExAblate therapy bed in a selected position according to the planned treatment area. The patient's area of treatment may be placed in a special-purpose imaging coil and positioned in the magnet in the treatment position.
6. An MRI scan will be performed with T2 weighted sequence in all three orientations to localize and measure the target tumor to be treated (other sequences are allowed should they be needed).
7. The skeletal structure in the treatment area will be evaluated to identify any abnormal anatomy that could prevent safe treatment. Adjacent organs will be evaluated to ensure that no bowel, lung or major nerves are in close proximity to the treatment area, or that other obstructions are present in the pathway of the ultrasound treatment beam. Any prior scar will be identified on the image and the ultrasound treatment plan will be planned to avoid sonicating through the scar whenever possible.
8. If the bone metastasis to be treated is identifiable on the MR images, accessible by the device for treatment, and the patient meets all inclusion and exclusion criteria, treatment planning will begin.
9. The physician will trace the contour of the bone cortex in the targeted area
10. The physician will draw the treatment volume using MR images from one or more scan orientations using the following guidelines:
 - a) Only one well defined lesion can be treated.
 - b) Three most painful lesions are to be evaluated separately at baseline and throughout the pre-treatment period.

- c) The targeted lesion must be at least 2 points more painful on the NRS compared to other painful lesions.
- 11. A central point on the soft tissue-bone interface of the targeted bone (depending on patient anatomy) will be sonicated with a low thermal dose, generating sub-lethal sonication, to verify targeting accuracy in the patient. Target placement and transducer positioning will be adjusted as necessary.
- 12. If at this point it is determined that the patient cannot be treated, he or she will be withdrawn from the magnet and the IV line, catheter if inserted and pulse oximeter will be removed. The patient will be taken to the recovery area for observation and release. Follow-up will consist of a phone call at 1-week post treatment. These patients will be considered screen failures, and will not be included in either the safety or efficacy analyses.
- 13. As part of our treatment procedure Geometric Verification in soft tissue is performed to confirm that the thermal location of the planned sonication spot is accurate. Geometric Verification is used to correct any residual geometric errors. According to the treatment guidelines the procedure will be terminated if no MR thermal signal is observed during this verification phase. Termination of treatment at this phase is before the planned therapeutic dose is administered. These patients will be considered screen failures and will not be included in the efficacy analysis.
- 14. Treatment will begin. Sonications will be performed on successive points [sonication duration between 15 – 60 sec]. The effect of each sonication will be measured by MR using phase map imaging, reflecting the temperature-dependent change in the proton resonance frequency. Energy will be adjusted throughout the treatment, to achieve temperature between 65°C and 85°C from MR thermal images at the bone-soft tissue interface.
 - a) Prior to the delivery of any treatment sonications, all patients **MUST** be adequately sedated for the treatment. Failure to adequately manage the patient may lead to unnecessary intra-procedure sonication related pain events. For this study, **ALL** patients must receive adequate level of local medication, for example, intercostal nerve block; failure to manage patients may also lead to under treatment. Note: equivalent methods of patient management may also be performed per local site standards.
 - b) Monitoring of heart rate and pO₂ saturation will be maintained throughout the procedure
 - c) During treatment, the nominal setting of the average of energy density for all treatment is set for 9 J/mm² ; While the treating

physician still has the ability to tailor the energy during the treatment, it should be noted that 1) lower energy densities may lead to under-treatment, 2) high energy levels requires appropriate anesthesia regimen selection to ensure patient comfort.

15. Sonifications will continue until the prescribed targeted area has been treated. The goal is that the total time from 1st to last therapeutic sonication will be limited to 180-minutes, or to patient tolerance.
16. **If no more than 3 planned sonifications can be performed using therapeutic energies**, then these patients will be considered as screen failures, and will NOT be included in the intent-to-treat analysis. However, they will be added to the Safety analyses
17. Criteria to terminate treatment include patient intolerance to the treatment, targeting difficulties due to patient motion or a decision of the treating physician
18. Immediately post-treatment, a series of MR scans will be performed. The scanning will include T2 weighted sequences and T1 weighted contrast enhanced sequences to evaluate general anatomy and to assess treatment effect.
19. The patient will be taken off the therapeutic table and escorted to a recovery area for observation period pending release from hospital.
20. All imaging exams taken during the study will be archived for later analyses
21. If during the treatment session, the physician did not complete the planned treatment, and determines that it would be to the benefit of the patient to continue treatment at a second session, a second treatment session may be completed within two (2) weeks of the first treatment. However, only one painful site can be treated under this protocol and the purpose of the second treatment is to complete the original treatment plan. This protocol does not allow for a second treatment due to continued pain at the treated site or the treatment of additional painful lesions. The preparation procedures for the second treatment will be the same as the first, beginning with Step 4.3.2 above. No more than two treatments should be performed within a two (2) week period.

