2.4 Study End Points

Safety

A full safety profile will be developed for the ExAblate treatment of bone metastases. All adverse events will be captured and summarized as defined in **Section-6.2**. Adverse events (type, frequency, severity) are expected to be similar to those captured for the original PMA study (PMA # P110039).

For his study, the Safety comparison with the data of the Pivotal (IDE Study G070022) study will be descriptive with no statistical endpoints.

Efficacy

A full efficacy profile will be developed for the ExAblate treatment of bone metastases. For this study efficacy will be determined by comparing outcomes at the 3 month visit to baseline within subjects. Additionally the safety and efficacy of treatment Responders and Non-Responders will be tabulated, and compared with that of the original PMA (P110039).

The primary endpoint is the proportion of responders at the 3 month study visit.

Definition of terms:

- Patient Responders: these are all ExAblate treated patients who experience at least a 2 point improvement from baseline on NRS at the treated site without increase in medications
- Patient Non-Responders: these are all ExAblate treated patients who experience less than 2 points improvement from baseline to 3 months on the NRS at the treated site without increase of medication or increased medications.
- Patient Pain Progression: these are all ExAblate treated patients who either experience 2 points worsening from baseline to 3 months on the NRS at the treated site or who increase morphine equivalence 25% or more. Pain progression is a subset of non-responders.

Secondary Endpoints

This study has two secondary end points. The goal of these secondary end points is to assess the impact of the ExAblate treatment of painful bone Mets on the overall quality of life and clinical benefits to ExAblate MRgFUS treated patients:

Quality of life outcomes of all treated patients will be captured during the course of the study. A comparison between baseline and 3 months post-ExAblate treatment of the BPI-QoL will be performed.

Pain Medications of all patients will be captured and summarized. Changes in narcotic medications will be expressed in morphine equivalents.

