5.3 Missing Data

Analyses will be performed on both observed and data with missing values imputed per the method of last observation carried forward (LOCF) where data for missing visits is assigned the value of the previous visit. Analyses will include the presentation of results calculated based on the intent-to-treat principle.

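### Step 16 of Section 4.3 takes patients out of the intent-to-treat analysis after treatment has begun, which conflicts with Sections 2.4 and 5.3 and can overstate the responder proportion

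*Combined protocol and SAP*

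**What the plan says.** Section 4.3 runs in numbered steps. Step 11 gives a sub-lethal test sonication. Step 12 deals with patients found at that point to be untreatable: they are called screen failures, get one phone call at 1 week, and are left out of both safety and efficacy. Step 13 is a geometric verification; patients stopped there are also called screen failures and are left out of efficacy, with nothing said about safety.

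Step 14 then states "Treatment will begin. Sonications will be performed on successive points". Step 16 covers patients in whom no more than 3 planned sonications could be performed at therapeutic energies: "these patients will be considered as screen failures, and will NOT be included in the intent-to-treat analysis". It adds "However, they will be added to the Safety analyses". Step 17 reads "Criteria to terminate treatment include patient intolerance to the treatment, targeting difficulties due to patient motion", and also allows stopping by decision of the treating physician. Step 21 provides that "a second treatment session may be completed within two (2) weeks of the first treatment" if the planned treatment was not completed.

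Section 2.4 makes the proportion of responders at 3 months the primary endpoint and defines responders thus: "these are all ExAblate treated patients who experience at least a 2 point improvement from baseline on NRS". Non-responders and pain progression are defined over the same treated population, with no minimum number of sonications. Section 5.3 says "Analyses will include the presentation of results calculated based on the intent-to-treat principle" and does not define the set.

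**The concern.** The only place that says who is in the intent-to-treat set is step 16, and it removes people by what happened after treatment started. Three things follow.

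- A patient with 1, 2 or 3 therapeutic-energy sonications is a treated patient under Section 2.4 and a screen failure under step 16. Both cannot govern the primary endpoint.
- Because treatment may be stopped for intolerance, motion or physician judgement, entry to the primary analysis can depend on how the procedure went, in an open single-arm study. If patients stopped early respond less often than those analysed, the reported proportion is too high. That proportion is also to be tabulated against the original PMA data.
- Step 16 does not say whether the count of 3 covers one session or both when step 21 applies, so two analysts could build different sets.

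A secondary matter concerns safety. Patients stopped at step 12 have had an IV line and a test sonication, yet they are left out of the safety analysis. Section 2.2 counts device-related complications from the first treatment day, and Section 6.2 puts all treatment side effects in the final analysis.

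**Working it through.** **The plan's own figure.** Section 5.2 gives 65 subjects for a McNemar test with 60% responders, 30% progressors, one-sided alpha 0.025 and power 0.70. The normal approximation is n = [1.960·√0.90 + 0.524·√(0.90 − 0.30²)]² / 0.30² = 60.4, so 61. Exact power at 65 is 0.693, and the first n with exact power of at least 0.70 is 67. The stated 65 is reproduced within tolerance and is not at issue.

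**Who is removed.** No more than 3 includes zero.

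| Therapeutic-energy sonications | Section 2.4 | Step 16 |
|---|---|---|
| 0 | arguably not treated | out of intent-to-treat |
| 1 to 3 | treated | out of intent-to-treat |
| more than 3 | treated | in |

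The conflict is clear in the middle row and weaker in the first.

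**Effect on the responder proportion.** No step 16 rate is given, so the number restored, k, and their response rate, r, are assumptions. Take 70 analysed at the plan's rates: 0.60 × 70 = 42 responders and 0.30 × 70 = 21 progressors. With k restored, the proportion is (42 + r·k)/(70 + k).

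The nearest documented figure is in Section 1.4: 1 of 10 feasibility patients could not complete treatment because of device access (10%, exact 95% CI 0.3% to 44.5%). That is not a step 16 rate and only suggests a range. A 10% share gives k = 70 × 0.1/0.9 = 7.8, rounded to 8.

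| k | r = 0 | r = 0.30 | r = 0.60 |
|---|---|---|---|
| 3 | 57.5% | 58.8% | 60.0% |
| 5 | 56.0% | 58.0% | 60.0% |
| 8 | 53.8% | 56.9% | 60.0% |
| 10 | 52.5% | 56.3% | 60.0% |

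**Effect on the primary test.** The test uses only responders and progressors. The one-sided exact sign-test p is P(X ≥ responders), with X binomial(responders + progressors, 0.5).

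| Restored patients | Responders vs progressors | p |
|---|---|---|
| none | 42 vs 21 | 0.0056 |
| 10 at planned rates (6 and 3) | 48 vs 24 | 0.0032 |
| 4, all progress | 42 vs 25 | 0.0249 |
| 5, all progress | 42 vs 26 | 0.034 |
| 8, all progress | 42 vs 29 | 0.077 |

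Restored patients who neither respond nor progress leave p unchanged but lower the proportion.

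**Safety.** No step 12 rate is given either. One event in one omitted patient would change 0/70 into 1/71 = 1.4%. This shows what the denominator rule does and predicts nothing.

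**The case against.** The best defence is that step 16 is a prespecified minimum-exposure rule, fixed before any 3-month outcome is known. Section 1.3 says about 30 sonications are typical, so 3 is roughly a tenth of a treatment. The wording suggests feasibility, Section 2.4 never defines treated, and a single-arm study has no randomisation to protect. Part of this stands: such a rule is acceptable for a modified or per-protocol set, and some late stops may be true access failures. But step 16 does not separate those from intolerance, and renaming the set would leave the primary endpoint on patients selected by how the procedure went. It is fair to add that requiring one therapeutic-energy sonication still conditions on the procedure to a small degree, which is why a supportive analysis is needed.

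Three stronger readings are tempting and are not supported.

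- A reader might infer that step 12 flatly contradicts Sections 2.2 and 6.2. Section 2.2 names no population, Section 6.2 concerns treatment side effects, and step 12 patients can be read as never treated. Adverse events may still be recorded under Sections 6.3 and 6.5. What is lost is their place in the safety summary and denominator.
- A reader might infer that steps 12, 13 and 16 set three different safety rules. Step 13 excludes only from efficacy, so by contrast with step 12 its patients most naturally stay in safety. The plan just does not say so.
- A reader might infer that 3-month data on step 16 patients will exist anyway, because Section 4.4 schedules visits for all patients. Sections 4.1 and 4.2 exit patients who do not qualify as screen failures, and step 16 applies that label, so the data are not assured.

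**Conclusion.** The concern holds for the efficacy set. For patients with 1 to 3 therapeutic-energy sonications, step 16 conflicts with Sections 2.4 and 5.3, and nothing else in the plan resolves it. The direction of any bias is upward if those patients respond less often. Its size is unknown and may be zero.

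The illustration of 60.0% falling to 53.8% rests on 8 restored patients, none responding, and 70 analysed at the planned rates. It should not be read as an estimate. Nor should a reader infer that the primary test is immune: it holds at the planned rates but passes 0.025 once five restored patients all progress with no added responder.

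The safety point is secondary. Step 12 sits poorly with the Section 2.2 window, and with Section 6.2 if a patient given only the test sonication has a side effect. The plan is unclear there rather than plainly contradictory. Overall this should be fixed before analysis. The textual conflict is certain, its effect is not, and the repair is cheap.

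**What to change.** - Delete the intent-to-treat exclusion in step 16. Define the primary efficacy set as every patient who received at least one therapeutic-energy sonication, counted across both sessions where step 21 applies.
- Add a supportive analysis that includes patients in whom step 14 was begun but no therapeutic-energy sonication was achieved.
- Keep the set with more than 3 sonications as a per-protocol sensitivity analysis.
- State that step 16 patients are not exited as screen failures and complete the Section 4.4 visits. Apply the Section 5.3 rules (observed data and last observation carried forward) to them as to everyone else.
- Define the safety set as every patient who received any sonication, including those at steps 11 and 13. Report step 12 patients over the follow-up they have, and state the safety status of step 13 patients.
- Tabulate numbers and reasons for stopping at steps 12, 13 and 16, separating device access from intolerance, motion and physician decision.

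The cost is protocol and SAP wording, one extra table and 3-month data on a few more patients. The reported responder proportion may be slightly lower. None of this alters when or why treatment is stopped.

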4.4 Follow-up

The follow-up visits of all patients will be completed at 1 week and 1, 2 and 3 months post-ExAblate treatment. Patients will be evaluated for general health, efficacy measurements as well as for device/procedure related AEs that may have occurred during the follow-up period. Additional data regarding dosage and frequency of analgesic intake for the management of the

metastatic bone tumor induced pain will also be collected. Following treatment the study staff will mark the treatment NRS form indicating the place where the treatment was performed. These marked questionnaires will be provided to the patient to complete by the study staff for each time point in the follow up. The patient will be instructed to indicate the change of pain at the place of treatment. Although the 1-Week, 1-Month, 2-Month and 3-Month visits are office visits, and in view of the patient population general health may change at any given time due to the underlying cancer disease, participating sites may use their discretion to make the visit(s) a phone visit to accommodate the patient best interest. However, all attempts should be made to ensure an office visit. The visits will be used to evaluate the patient's NRS, BPI-QoL, and KPS, pain medication intake, symptoms and their general health, including any safety related issues and any changes in symptoms following treatment. For phone visits, study personnel will contact the patient, inquire about AEs and question the patient according to the pain questionnaire, and pain medication intake, and fill it out in parallel. Because the KPS is a physician completed assessment it may not be required for visits completed by telephone. The study personnel will then sign and date the completed forms.

All pre-treatment and post treatment MR and CT images will be de-identified and archived, and then will be forwarded to the Sponsor

4.5 Study Requirements and Visit Schedule

The tables below summarize the data that will be captured during the course of this study.

Table 1: Study Visits

	Window Allowance	Imaging	Questionnaire s	Additional Data
Enrollment	N/A	CT**	PE, NRS, BPI, KPS	Freq. and dosage of analgesics.
Run-in Visits:			NRS, BPI, KPS	Freq. and dosage of analgesics.
Visit #1 Baseline MR Imaging and ExAblate Treatment (2 nd session permitted).	On Run-in Visit 2 or within 1-week ± 3 days of Run-in	MR	NRS, BPI, KPS	Freq. and dosage of analgesics.
Visit #2 (office): 1-Week Post-Tx	± 3 days		PE, NRS, BPI, KPS	Freq. and dosage of analgesics.
Visit #3 (phone): 1-Month Post-Tx	± 1 Week		NRS, BPI, KPS	Freq. and dosage of analgesics.
Visit #4 (phone) 2-Months Post-Tx	± 2 Weeks		NRS, BPI, KPS	Freq. and dosage of analgesics.
Visit #5(office) 3-Months Post-Tx	± 2 Weeks		PE, NRS, BPI, KPS	Freq. and dosage of analgesics.
**May be completed at any visit before treatment.				

5 STATISTICAL ANALYSIS PLAN

This study is a designed as a single arm within subjects comparison of outcomes at the 3 month visit to baseline. For this study, a total of 70 patients meeting approved

commercial guidelines for bone metastases will be enrolled and treated with the ExAblate system at from 7 to 10 investigational sites.

Safety

A full safety profile will be developed for the ExAblate treatment of bone metastases. All adverse events will be captured and summarized as defined in **Section-6.2**. Adverse events (type, frequency, severity) are expected to be similar to those captured for the original PMA study (PMA # P110039). For this study, the Safety comparison will be descriptive with no statistical endpoints.

Efficacy

A full efficacy profile will be developed for the ExAblate treatment of bone metastases. For this study efficacy will be determined by comparing outcomes at the 3 month visit to baseline within subjects. Also, the outcomes will be compared with the original efficacy data of the PMA (P110039), where the proportion of treatment Responders and Non-Responders will be tabulated and compared.

The statistical hypothesis is that the proportion of responders will be significantly greater than the proportion of subjects experiencing pain progression (worsened pain or increased pain medications usage) by at least 30% or an odds ratio of at least 2.

Secondary Endpoints

Medications use and quality of life will be analyzed as secondary endpoints.

PATIENT GENERAL HEALTH STATUS

Patient overall quality of life status will be assessed by the BPI-QoL Pain Interference scale which will be administered pre-treatment and post-treatment. The trajectory of change may be analyzed descriptively by regression slopes.

BASELINE DATA ANALYSES

Baseline clinical, demographic and patient reported outcome characteristics will be tabulated and compared descriptively to the original PMA.

HEALTH COST AND SERVICES UTILIZATION

Summary tabulations and figures may be developed for reimbursement purposes only.

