2 OBJECTIVES

2.1 Background

As part of the PMA # P110039 review process and approval, InSightec was requested to conduct a post-approval study. Patients will be treated following the approved commercial treatment guidelines.

For this study, participating sites will use the ExAblate device for the administration of the ExAblate treatment. This study will be performed on either 1.5T or 3T MR scanners.

For this study, a total of 70 patients meeting the approved commercial guidelines will be enrolled and treated with the ExAblate system at from 7 to 10 sites. The proportion of responders is expected to be at least 30% greater than the proportion of subjects experiencing pain progression (i.e., 60% vs. 30%). Additionally, at the 3 month visit, an analysis of both the safety and efficacy profiles will be compared to the original PMA pivotal study group. This comparison will be descriptive with no statistical endpoints.

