5.2 Statistical Considerations and Sample Size

The primary goal of the study is to evaluate the safety and efficacy of the ExAblate palliative treatment of painful bone metastases. This study will be conducted with both the 1.5T and 3T MR scanners. Seventy (70) patients will be enrolled and treated; enrollment will continue at from 7-10 research sites.

A sample size analysis was performed using the McNemar Test Power Analysis from the PASS² program using parameters from the pivotal PMA study (PMA # P110039). The response rate in the USA was 18/30 = 60%. The proportion of non-responders experiencing pain progression was 30%. Thus, the proportion discordant was 90%. Given $\alpha = 0.025$ for a one-sided hypothesis, $1 - \beta = 0.7$ requires a sample size of 65 subjects to detect an odds ratio of 2.0. The odds ratio is equivalent to a difference between two paired proportions of 0.30 which occurs when the difference in the proportion of responders (60%) is 30% greater than the proportion of subjects experiencing pain progression (30%). In order to account for potential dropouts 70 subjects will be initially enrolled in the study.

The hypothesis can be specified as follows:

$H_0: P10 = P01$. $H_1: P10 > P01$, where $P10$ is the proportion of subjects that respond (improve by 2 points without increasing medications) and $P01$ is the proportion of subjects that worsen.

Subject Confidentiality

Subject confidentiality will be maintained throughout this study, including all publications. Data collected and entered into the CRFs are the property of the study sponsor. Representatives from the study sponsor or authorized sponsor representatives, the Institutional Review Board (IRB), Ethics Committee or the FDA may receive copies of the study records and may review medical records related to the study.

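### Section 5 puts a 30-point or odds-ratio-2 advantage inside the statistical hypothesis, but Section 5.2 tests plain equality, and only the 5.2 version fits 65 subjects and 70% power

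*Combined protocol and SAP*

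**What the plan says.** Three places use the same figures in different roles.

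- **Section 5, Efficacy** gives the statistical hypothesis: responders significantly exceed subjects with pain progression "by at least 30% or an odds ratio of at least 2".
- **Section 5.2** formally specifies H0: P10 = P01 against H1: P10 > P01, where P10 is the proportion responding and P01 the proportion worsening. There is no margin. The figures appear there as the effect to detect: the calculation "requires a sample size of 65 subjects to detect an odds ratio of 2.0". It adds: "The odds ratio is equivalent to a difference between two paired proportions of 0.30", tied to 60% responding and 30% progressing.
- **Section 2.1** treats the 30% as a forecast: the responder proportion "is expected to be at least 30% greater than the proportion of subjects experiencing pain progression", with 60% versus 30% given as the case in mind.

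No section says that an observed difference of 30 points, an observed odds ratio of 2, or a confidence limit beyond either is needed for success.

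**The concern.** The plan states its one inferential hypothesis twice, and the two statements differ. Section 5.2 and Section 2.1 agree that 30 points is what the sponsor expects, so Section 5 is the outlier. Read literally, Section 5 could mean either of two things, and it does not say which:

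- significance plus an observed result of at least 30 points or odds ratio 2; or
- a test against a null margin of 30 points or odds ratio 2.

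The two figures joined by *or* are also not one criterion, since they coincide only at one level of discordance.

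The null, alternative and alpha are prespecified in 5.2, so the main risk is over-claiming: a rejection of P10 = P01 reported as confirming the Section 5 hypothesis. If the Section 5 words are instead given effect, the stated 70% power no longer applies.

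**Working it through.** **Inputs, all from Section 5.2.** One-sided alpha 0.025; target power 0.70; P10 = 18/30 = 0.60; P01 = 0.30; discordance 0.60 + 0.30 = 0.90; odds ratio 0.60/0.30 = 2.0; N = 65, with 70 enrolled to allow for dropout. The plan does not say whether the McNemar test is exact; the exact form is used below unless stated.

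**1. Reproduce the plan's figure (H0: P10 = P01).** Let D ~ Bin(n, 0.90) be the number of discordant subjects, b ~ Bin(D, 0.60/0.90 = 2/3) the responders and c = D − b the progressors. Reject when P(Bin(D, 0.5) ≥ b) ≤ 0.025, and average over D.

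- n = 65: power 0.6925. n = 70: power 0.7297. The smallest n reaching 70% is 67.
- The uncorrected asymptotic test gives 0.731 and 0.769.
- The usual normal approximation gives n = (1.960·√0.90 + 0.524·√(0.90 − 0.30²))² / 0.30² = 60.4, so 61.

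The stated 65 subjects and 70% are reproduced by the exact test to within 1 point of power.

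**2. Power at 60% versus 30% under each reading of Section 5.**

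| Reading | n = 65 | n = 70 |
|---|---|---|
| Section 5.2: H0: P10 = P01 | 69.3% | 73.0% |
| Significance plus observed b − c ≥ 0.30n or b ≥ 2c | 53.2% | 54.4% |
| Null margin, odds ratio 2 (exact, null probability 2/3) | 1.7% | 1.8% |
| Null margin, difference 0.30 (Wald lower limit above 0.30) | 3.6% | 3.5% |

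The last two rows are simply the size of each test, since the planning effect lies on the margin. A larger sample does not cure that.

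**3. Wins under 5.2 that miss both Section 5 figures, at the planning effect.**

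- n = 65: (0.6925 − 0.5321)/0.6925 = 0.1604/0.6925 = 23.2%.
- n = 70: (0.7297 − 0.5441)/0.7297 = 0.1856/0.7297 = 25.4%.

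Example: 37 responders and 21 progressors of 65 give one-sided p = 0.024, a difference of 16/65 = 24.6 points and odds ratio 37/21 = 1.76.

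**4. The two figures joined by *or*.** With odds ratio 2, P10 = (2/3) × discordance and P01 = (1/3) × discordance, so the difference is discordance/3: 30.0 points at 90%, 26.7 at 80%, 23.3 at 70%. At 90% discordance the two thresholds disagree in about 5% of wins. If discordance were 80% with odds ratio 2 (an assumption, not a figure in the plan), they would disagree in 22.8% of wins at n = 65 and 18.2% at n = 70. Example: 38 versus 18 of 70 gives one-sided p = 0.005 and odds ratio 2.11, but a difference of 20/70 = 28.6 points.

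**5. A result exactly on plan: 42 versus 21 of 70.** One-sided p = 0.0056.

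- Difference 21/70 = 0.30, SE = √((0.90 − 0.09)/70) = 0.1076, 95% CI 0.30 ± 1.96 × 0.1076 = 8.9 to 51.1 points.
- Odds ratio 42/21 = 2.0. The Clopper-Pearson interval for 42/63 is 0.537 to 0.780, which as odds gives 1.16 to 3.56.

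Even this result rules out neither an advantage well below 30 points nor an odds ratio well below 2.

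**The case against.** The strongest reply is that the plan largely settles the matter itself. Section 5.2 gives the formal null, alternative and alpha; Section 5 is prose leading into it; Section 2.1 confirms that 30 points is an expectation; and 5.2 ties the equivalence of odds ratio 2 and 0.30 to the 60%/30% case, so *or* most naturally reads as two expressions of one effect. On this view the low power under a margin only shows that no margin was planned. The 23% to 25% of wins below the planning effect, and the wide intervals, are ordinary features of a superiority test of this size. The 18% to 23% disagreement rests on an assumed 80% discordance. No section commits the sponsor to claiming a 30-point advantage. Finally, 5.2 names McNemar only for the power calculation.

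Much of this stands. Section 5.2 is very probably what was intended, the sample size is not in error, and the margin figures measure test size rather than harm. But likely intent does not remove the conflict. The passage introduced as the statistical hypothesis contains an effect size that the formal test does not examine, so 5.2 would call 37 versus 21 of 65 a success while Section 5, read as written, would not. Taking McNemar as the analysis test is an inference, though a reasonable one: it is the only test the plan powers.

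**Conclusion.** The point holds and should be fixed. As written, the Section 5 hypothesis is one that 65 subjects and 70% power do not support and that a significant 5.2 result would not establish. Against the 5.2 null, power is 69.3% (n = 65) to 73.0% (n = 70). With an observed threshold added it falls to 53% to 54%, and as a margin test to about 2% to 4%. About a quarter of 5.2 wins at the planning effect miss both Section 5 figures.

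These results assume the plan's 60%/30% rates and, apart from the Wald margin row, the exact test. The uncorrected asymptotic form raises the 5.2 power to 73% to 77% and leaves the conflict as it is. Confidence in the inconsistency is high. Its practical effect is mainly on what may be claimed from a positive result.

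**What to change.** - In Section 5, state the 5.2 hypothesis: H0: P10 = P01 against H1: P10 > P01, one-sided McNemar test at 0.025. Say whether the test is exact. Remove the 30% and odds-ratio-2 clause from the hypothesis.
- In Section 5.2, label 0.30 and odds ratio 2 as the planning alternative, equivalent only at 90% discordance.
- Report P10 − P01 and the odds ratio with 95% confidence intervals, and claim a 30-point or two-fold advantage only if the lower limit exceeds it. This goes a little beyond correcting the wording, but it closes the route to over-claiming.
- If a margin or observed threshold was really intended, name one scale and restate the power for it.

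The cost is wording in Sections 5 and 5.2, plus two intervals in the report. The sample size, test, data and population do not change. The downside is a narrower claim: responders exceed progressors, and nothing larger unless the interval supports it.
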